3.2.1 Rationale for patient population, doses and design

This study will be conducted in patients with advanced solid malignancies. This population has been chosen to obtain safety, tolerability and PK data in a patient population relevant to further studies and future use of this compound.

This is the first study of AZD8931 in cancer patients and as such follows a conventional sequential dose escalation design. The number of evaluable patients to be enrolled is based on the desire to gain adequate information whilst exposing as few patients as possible to the study medication and procedures.

There are no data to indicate that the safety and tolerability of AZD8931 will differ significantly in patients with different types of tumour. An “all comers” population of patients with advanced solid malignancies are therefore eligible to enter this part of the study.

The design of this study takes into account the anticipated patient population to be enrolled and the emerging toxicity profile of AZD8931.

The starting dose of AZD8931 proposed for this study is 40 mg twice daily. Experience with AZD8931 and other EGFR inhibitors suggests that the parameter that predicts for corneal toxicity (the DLT in dog studies) is cumulative drug exposure (area under plasma concentration-time curve [AUC]) rather than dose. Thus selection of a starting dose for the study took into consideration a comparison between the predicted exposure in humans and the exposure observed in the toxicity studies in the dog. The starting dose for this study was determined to be 40 mg twice daily, which is predicted to produce a cumulative AUC that is 2 to 8-fold lower in patients than observed at the no effect level in the dog 1-month study. At 40 mg twice daily, approximately 40% of individuals would be predicted to have plasma

concentrations maintained continuously above the AZD8931 IC₅₀ (concentration for 50% inhibition) for EGFR, about 10% above the value for phosphorylated ErbB3 and none above the IC₅₀ of ErbB2. However, 10% of individuals would be predicted to exceed the ErbB2 IC₅₀ for 8 hours in every 12-hour dosing interval. Thus 40 mg twice daily could be considered sub-therapeutic in respect of all of the key targets of AZD8931, but possibly still capable of eliciting some pharmacological action. On the assumption that the IC₅₀ values used in these predictions are valid, it would be predicted that a therapeutic dose should be achieved for a significant proportion of patients after one or two dose escalations.

The escalation will be by dose doubling unless the SMC decide, on the basis of observations in the patients, that an alternative (eg, a smaller escalation) is warranted. The rationale for the proposed starting dose is provided in Section 1.1.2. The study is designed to gain safety and tolerability data whilst exposing as few patients as possible at each dose level.

Administration of a single dose of AZD8931 followed by an observation period (of 4 to 6 days) will allow single dose PK data to be collected. PK samples will also be collected after 14 days of twice daily dosing to allow investigation of the PK after multiple dosing. The 21-day repeat dosing period should permit adequate assessment of safety and tolerability data.

A dose doubling strategy will be employed as this prioritises the safety and well being of the patients by escalating the dose in a relatively cautious manner but reaching a non-tolerated dose level in the minimum possible number of dose increments. Dose escalation will take into account emerging safety, tolerability and PK data but will not exceed a doubling in dose at any dose increment.

Based on emerging data, including PK and/or safety data and/or pre-clinical data, the SMC can consider alternative schedules, including once-daily dosing, in consultation with AstraZeneca and

There will be an adequate period between dose groups to allow collection and review of relevant safety and PK data by the SMC prior to dose decisions.

3.2.2 Rationale for inclusion, exclusion criteria, stopping criteria and monitoring

As stated in Section 1.1.1, dosing with AZD8931 to non-clinical species has raised the following as potential safety concerns: corneal epithelial ulceration, arrhythmia, hyperkalemia, hyperglycemia, hypotension, epithelial degeneration, and phototoxicity. The relevance of some of these findings to humans is not clear and these will be carefully monitored during the study and specific stopping criteria have been defined in the protocol.

Specific ophthalmologic exclusion criteria have been incorporated into the study design to limit confounding morbidity. A robust ophthalmologic monitoring will be considered, including a schedule of ophthalmic examinations with frequent symptomatic follow-up with additional corneal examinations if indicated.

QT prolongation (prolongation of interval from the beginning of the QRS complex to the end of the T wave) and arrhythmia were not considered to be a risk in study D0102C00001, as the

free AUC exposure limit for this study is more than 30-fold below the level at which pro-arrhythmia was identified in non-clinical studies. No clinically significant QT or cardiac arrhythmia related safety concerns were noted up to a single dose of 200 mg in healthy volunteers. However, any potential effects of AZD8931 on the QT interval in man will be closely monitored in this patient study. Patients with a baseline QTc interval in excess of 460 msec will be excluded from participation in the study. Digital ECG monitoring will be performed during the study, particularly around time points where C_{max} is anticipated to occur on the first day and at steady state. The ECGs will be reviewed on site for the SMC decision making. In addition ECGs will be reviewed centrally for formal analysis of QT liability.

Based on non-clinical data, blood pressure, potassium and glucose were monitored intensively in study D0102C00001. No significant findings were noted up to 200 mg. Patients in the MAD study will be monitored for BP changes through frequent measurement of blood pressure, particularly around the time of C_{max} after dosing on the first day and at steady state, and will be monitored for potassium and glucose particularly at time points around where C_{max} is anticipated to occur.

Patients with random blood glucose above 11.1 mmol/L at screening will be excluded from the study. Those with impaired glucose tolerance would be included only if their fasting blood glucose levels are recorded within non-diabetic ranges. Blood glucose levels will be monitored during the study. In the event of a patient developing significant hyperglycemia (fasting glucose >13.9 mmol/L), that cannot be attributed to any other cause, this will be deemed as a DLT. The evaluation of post-prandial glucose as an assessment of a patient's glycemic state in this study population may be confounded by disease burden, concomitant medications (steroids), study conditions (food restrictions, disturbed circadian activity, mobility etc). The clinical picture of day-to-day glycemic state obtained from random pre- and post-dose glucose samples may not reflect the true glycemic state.

Patients with history or evidence of cardiac dysfunction will be excluded from the study and a baseline echocardiogram and digital ECG will be used to reference any symptomatic or non-symptomatic deterioration in cardiac function that may happen during the study.

Patients with history or evidence of interstitial lung disease will be excluded from the study and baseline radiology will be used to compare the findings associated with any respiratory symptoms later in the study.

Patients in this study will be advised of the need for sun protection measures such as avoidance of sun beds, the application of sun-cream (sun protection factor [SPF] minimum 15) to body parts exposed to the sun, and the use of sunglasses in sunny conditions. Patients will be advised to adopt such measures for a period of 3 months after receiving their final dose of AZD8931.

No reproductive toxicology studies have been conducted to assess safety to the human foetus. AZD8931 has not shown any genotoxic potential. It is not known whether AZD8931 or its metabolites are secreted in human milk or semen. Therefore, until further data is available, AZD8931 is not suitable for administration to pregnant or nursing women, and conception

while on treatment must be avoided. For AZD8931 studies, male subjects will be required to abstain from unprotected sex and sperm donation for 4 months following dosing, and will be advised to use condoms in addition to a second reliable form of contraception for a specified period.

Finally, all safety data will be collected on a regular basis and reviewed by the principal investigator.

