The non-validated PK results showed that AZD8931 is orally bioavailable over the dose range 2.5 mg to 200 mg. Absorption was moderately rapid with time to reach maximum plasma concentration (t_{max}) occurring in most subjects at 1.5 or 2 hours after the dose (range 0.5 to 4 hours). After reaching the maximum plasma concentration (C_{max}), plasma concentrations declined biphasically. A terminal phase became apparent from about 24 hours after the dose,

when the plasma concentrations had fallen to around 6% of the peak values. The mean terminal elimination half-life ($t_{1/2}$) across the dose range was 12.1 hours (range 7.6 to 16.6 hours).

Based on the above data, it was determined that twice-daily administration should be employed in the current study to avoid excessive fluctuations between steady state (ss) C_{max} ($C_{ss_{max}}$) and minimum plasma concentration ($C_{ss_{min}}$). It is predicted that twice-daily dosing will lead to accumulation of study drug at about 30%, with a 5-fold fluctuation between $C_{ss_{min}}$ and $C_{ss_{max}}$.

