3.1.6 Study flow chart and study plan

Figure 2 Study flow chart

3 to 6 patients	Single dose	4-day observation period	Twice daily dosing for 21 days	Data collection /review	SMC review	Single dose	4-day observation period	Twice daily dosing for 21 days...
Day	D1		D5 to 7			(1)		
Repeat dosing day			R1.....R21					

(1) New dose group (increased dose, same dose, decreased dose) depending on result of SMC meeting to discuss previous dose cohort of 3 to 6 evaluable patients (see Section 6.6).

Abbreviations: SMC: Safety Monitoring Committee. Shading: AZD8931 treatment.

Table 1 Study plan

Assessments	Screening	DLT Evaluation Period ^a									Premature discontinuation	Continuation beyond R21 ^a	Post-study follow-up
		Single dose											
Day (h = hours)	D-21 to D0	D1	D2 (24 h)	D3 (48 h)	D4 (72 h)	D5 to D7						Every 3 weeks	7 days after last dose
Repeat dosing (R) day (d=day)						R1	R3	R7 ±1d	R14 ±1d	R21 ±1d	≤2d	±3d	±1d
Informed consent (main study, genetics [optional], proapoptotic biomarkers [optional])	x												
Inclusion/exclusion criteria	x												
Tumour TNM stage at diagnosis and at study entry (and ErbB2 status, if available)	x												
Tumour assessment (RECIST)	x ^b										x ^c	x ^d	
Chest X-ray	x												
Demographics	x												
Medical/surgical history	x												
Previous anticancer therapy, including surgery	x												
Urine pregnancy test	x												
Administer AZD8931		Single dose ^e				Twice daily for 21 days ^e						Twice daily ^e	
Physical examination	x										x		x
Dermatological examinations ^f	x									x	x		x ^g

Table 1 Study plan

Assessments	Screening	DLT Evaluation Period ^a									Premature discontinuation	Continuation beyond R21 ^a	Post-study follow-up
		Single dose											
Day (h = hours)	D-21 to D0	D1	D2 (24 h)	D3 (48 h)	D4 (72 h)	D5 to D7						Every 3 weeks	7 days after last dose
Repeat dosing (R) day (d=day)						R1	R3	R7 ±1d	R14 ±1d	R21 ±1d	≤2d	±3d	±1d
Ophthalmological assessments	x									x	x	x ^h	x ^g
Echocardiography	x									x	x	x ⁱ	x ^g
12-lead Electrocardiogram ^j	x	x ^k	x	x	x	x	x ^l	x ^l	x ^k	x	x	x	x
Vital signs (heart rate, blood pressure)	x	x ^k	x	x	x	x	x ^l	x ^l	x ^k	x	x	x	x
Blood sample for AZD8931 pharmacokinetic (PK) analysis		x ^k	x	x	x		x ^l	x ^l	x ^k				
Blood sample for clinical chemistry, haematology, coagulation parameters	x	x ^{l,m}	x	x	x	x ^l	x ^l	x ^l	x ^{l,m}	x ^l	x	x	x

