^j 12-lead electrocardiogram (ECG) after 10 minutes rest in the supine position. The patient should be examined using the same machine throughout the study. Digital ECGs for QTc interval analysis (days D1 and R14) must be in triplicate (one after another). Paper read-outs are sufficient for other assessments.

^k At pre-dose and at 1, 2, 4, 6, 8 and 12 hours post-dose (days D1 and R14).

^l Pre-dose.

Amended Clinical Study Protocol
Drug Substance AZD8931
Study Code **D0102C00002**
Edition Number 3
Date

- ^m Glucose and potassium only at 6 hours post-dose (days D1 and R14).
- ⁿ At 8 hours post-dose.
- ^o After confirmation of eligibility.
- ^p Daily.
- ^q The DLT evaluation period starts from the first administration of AZD8931 and continues until the completion of all assessments prior to cycle 2 see Section [3.1.2](#) for further information

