4.4 Safety measurements

4.4.1 Laboratory safety measurements

Blood and urine samples for determination of clinical chemistry, haematology and urinalysis parameters will be taken at the times given in the study plan (see [Table 1](#)). Additional safety samples may be collected if clinically indicated at the discretion of the investigator. The date and time of blood and urine sample collection will be recorded on the appropriate CRF.

Blood samples should be collected for all clinical chemistry and haematology parameters. Fasting samples are not required for this study (except if random blood glucose is >13.9 mmol/L then a fasting blood glucose [minimum 8 hours fast without sugar-containing drinks] is recommended to confirm hyperglycemia).

The laboratory assessments will be performed locally at each centre's laboratory by means of their established methods.

Glucose and potassium monitoring: On Days D1 and R14 a blood sample should be taken at 6 hours post-dose for measurement of potassium and glucose levels only. Additional monitoring of potassium should be undertaken if the patient receives drugs that may cause hyperkalemia. Hyperkalemia should be managed according to local standards. Hyperglycemia should be managed according to local standards.

Females of child bearing potential must give a sample of the first urine passed during the day (see [Table 1](#)) for a pregnancy test to be performed.

All laboratory safety analyses will be performed by a local laboratory.

The following laboratory variables will be measured:

Clinical chemistry

P – Urea
P – Creatinine
P – Glucose (fasting^b)
P – Sodium
P – Potassium
P – Calcium
P – Albumin
P – Total bilirubin
P – Alkaline phosphatase
P – AST
P – ALT
P – Gamma glutamyltransferase
P – Lactate dehydrogenase
P – Unconjugated bilirubin (if total bilirubin elevated)

Additional analyses at screening only

P – Activated partial thromboplastin time
P – International normalisation ratio
B – HbA1c

Haematology

B – Haemoglobin
B – Erythrocyte count
B – Haematocrit
B – Platelet count
B – Total leukocyte count
B – Mean cell haemoglobin concentration
B – Mean cell volume
B – Mean cell haemoglobin
B – Monocytes (absolute)
B – Eosinophils (absolute)
B – Basophils (absolute)
B – Neutrophils (absolute)
B – Lymphocytes (absolute)

Urinalysis

U – Glucose
U – Protein^a
U – Blood^a
U – Urine sediment microscopy (Crystals, Casts, Epithelial Cells, Leucocytes and Erythrocytes)

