4.6 Volume of blood sampling

The total volume of blood that will be drawn from each patient in this study is as follows:

Table 3 Volume of blood to be drawn from each patient

Assessment	Sample volume (mL)	Number of samples per patient	Total volume per patient (mL)
Pharmacokinetics	3.0	19	57.0
Safety ^a	c		144.0 ^d
Pharmacogenetics ^b	9.0	1	9.0
Cell death (proapoptotic) biomarkers ^b	3.0	6	18.0
Total (with optional samples)			228 ^d
Total (without optional samples)			201 ^d

INR = International Normalized Ratio

- a Including clinical chemistry and haematology (11 samples each per patient), glucose and potassium (6 hours post-dose on days D1 and R14) (2 samples per patient), and screening tests (INR etc.).
- b Optional sample.
- c Safety laboratory assessments will be performed locally at each centre's laboratory by means of their established methods. The blood volumes are therefore subject to site-specific change.
- d Approximate maximum volume.

For patients who continue dosing beyond the DLT evaluation period, a blood sample for laboratory safety analyses and an optional blood sample (3 mL) for proapoptotic biomarkers may be collected at each visit.

Extra blood samples may also be collected if, for example, additional samples are required for repeat safety assessments or additional PK assessment, but will be not greater than 10% more of the planned volume.

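### Section 3.2.2 promises potassium and glucose monitoring around Cmax, but no scheduled draw from D1 to R21 falls in the reported tmax range; the only sample within a dosing interval is at 6 h

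*Protocol*

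**What the plan says.** Section 3.2.2 lists hyperkalaemia and hyperglycaemia among the potential hazards raised by the non-clinical work. It says ECG and blood pressure will be followed closely around Cmax on the first day and at steady state, and that patients "will be monitored for potassium and glucose particularly at time points around where" Cmax is anticipated.

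Section 1.1.2 gives the only human tmax: Cmax was reached in volunteers at times "occurring in most subjects at 1.5 or 2 hours after the dose (range 0.5 to 4 hours".

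The operative schedule is the same in three places:

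- **Table 1**, in the row "Blood sample for clinical chemistry, haematology, coagulation parameters": pre-dose sampling on dosing days (note l), samples at 24, 48 and 72 h after the single dose, and note m, "Glucose and potassium only at 6 hours post-dose (days D1 and R14".
- **Section 4.4.1**: on D1 and R14 "a blood sample should be taken at 6 hours post-dose for measurement of potassium and glucose levels only".
- **Table 3, note a**: "glucose and potassium (6 hours post-dose on days D1 and R14) (2 samples per patient".

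For ECG, vital signs and PK, Table 1 note k reads "At pre-dose and at 1, 2, 4, 6, 8 and 12 hours post-dose (days D1 and R14".

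**The concern.** Section 3.2.2 is part of the risk/benefit argument for the study. It uses the same Cmax reasoning for ECG, for blood pressure and for potassium and glucose. The schedule follows through on the first two only. Confirmed grade 3 or higher hyperkalaemia and fasting hyperglycaemia are DLT criteria (section 3.1.5), and the SMC reviews laboratory data before each escalation (section 3.1.2). Anyone relying on section 3.2.2 would think that potassium and glucose had been observed near peak exposure at each dose level. They would not have been.

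Three features of the protocol add weight:

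- Section 1.1.1.3 says the glucose rises in dogs had reversed by 24 h, and that the insulin response looked weakened or absent especially at high plasma levels. On that pattern the 24, 48 and 72 h samples say little about a transient rise. The 6 h sample carries nearly all the post-dose information.
- The volunteer data stop at a single 200 mg dose. Doubling from 40 mg gives 80, 160 and then 320 mg, so the fourth level exceeds that experience, with twice-daily dosing and about 30% predicted accumulation.
- Food is barred from 2 h before to 2 h after dosing (section 3.3.4). A 2 h sample is therefore at least 4 h after food, whereas a 6 h sample may follow a meal. Section 3.2.2 itself warns that post-prandial glucose may be confounded.

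**Working it through.** **1. Reproduce the plan's own sample count.** Table 3 note a gives 11 chemistry samples plus 2 potassium/glucose samples. From Table 1 the chemistry samples are screening, D1, D2, D3, D4, R1, R3, R7, R14, R21 and post-study follow-up = 11. The two 6 h samples are separate. Both figures agree.

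**2. Count the draws from D1 to R21.** 11 + 2 − 2 (screening and follow-up) = 11.

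| Draw | Time since last dose | Within 0.5 to 4 h? |
|---|---|---|
| D1 pre-dose | none given yet | no |
| D1 6 h | 6 h | no |
| D2, D3, D4 | 24, 48, 72 h | no (3 draws) |
| R1 pre-dose | 4 days or more after the single dose | no |
| R3, R7, R14 pre-dose | about 12 h | no (3 draws) |
| R14 6 h | 6 h | no |
| R21 pre-dose | about 12 h | no |

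Total 11, of which 0 are in range. Chemistry at continuation, discontinuation and follow-up visits has no fixed time relative to dose and is left out.

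**3. Comparison.** Note k puts ECG, vital signs and PK at 1, 2 and 4 h: 3 in-range times per day × 2 days = 6.

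**4. Distance of the 6 h draw from tmax.** 6 − 2 = 4 h and 6 − 1.5 = 4.5 h for the usual tmax; 6 − 4 = 2 h for the latest observed.

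**5. Rough exposure at 6 h.** This is illustrative and assumes log-linear decline from the peak: C(6)/Cmax = exp(−k × (6 − tmax)).

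*Single dose.* Section 1.1.2 places the start of the terminal phase at about 24 h, "when the plasma concentrations had fallen to around 6% of the peak values", so k = ln(1/0.06)/(24 − tmax).
- tmax 2 h: k = 2.813/22 = 0.1279 per h; exp(−0.1279 × 4) = 60.0%
- tmax 1.5 h: k = 2.813/22.5 = 0.1250 per h; exp(−0.1250 × 4.5) = 57.0%
- tmax 4 h: k = 2.813/20 = 0.1407 per h; exp(−0.1407 × 2) = 75.5%

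*Steady state.* The predicted peak-to-trough ratio is 5, with the trough taken at 12 h, so k = ln(5)/(12 − tmax).
- tmax 2 h: k = 1.609/10 = 0.1609 per h; exp(−0.1609 × 4) = 52.5%
- tmax 1.5 h: k = 1.609/10.5 = 0.1533 per h; exp(−0.1533 × 4.5) = 50.2%
- tmax 4 h: k = 1.609/8 = 0.2012 per h; exp(−0.2012 × 2) = 66.9%

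A 2 h draw would be at the peak if tmax is 2 h. If tmax is 1.5 h it would be at exp(−0.1250 × 0.5) = 93.9% after the single dose and exp(−0.1533 × 0.5) = 92.6% at steady state. For tmax of 4 h a 2 h draw is on the rising limb and this model gives no value. Section 1.1.2 describes biphasic decline, so true 6 h values may be lower than these.

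**The case against.** The counts are not in dispute, but several objections deserve an answer.

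- **No consequence is shown.** The time of peak effect is unknown. Potassium rose during intravenous infusion in anaesthetised dogs and was not raised by oral dosing in conscious dogs. Dog glucose rises generally accompanied cortisol rises. Nothing proves that either analyte tracks plasma tmax. This stands, and it limits the point to a mismatch between the stated and the scheduled monitoring.
- **Counting 11 draws exaggerates.** Nine are general panels that were never meant to catch Cmax. This is fair. On the two draws added for these analytes, the count is 0 of 2, and the conclusion is unchanged.
- **Other safeguards exist.** ECGs at 1, 2 and 4 h could show a severe potassium effect. Extra monitoring is called for with drugs that affect potassium or glucose (section 3.4.6), and section 4.4.1 allows clinically indicated samples. Volunteers had no significant findings up to 200 mg. These reduce the risk, but they are indirect, conditional or discretionary, or come from single doses in healthy men. None is the scheduled monitoring that section 3.2.2 describes.
- **A 2 h random glucose cannot itself establish the DLT**, which needs a confirmed fasting value. That is true, and equally true of the 6 h sample. Either can prompt the fasting test.
- **The percentages rest on assumptions** and on preliminary volunteer data. That is also true, and the conclusion does not depend on them.
- **Rewording section 3.2.2 would also remove the contradiction.** It would, but by dropping the monitoring from the rationale rather than providing it.

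One could also read 6 h as near enough to Cmax. The protocol's own practice argues against that: the same wording for ECG and blood pressure is met with 1, 2 and 4 h assessments. No reason is given for choosing 6 h.

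**Conclusion.** The concern holds. Of the 11 scheduled potassium/glucose draws from D1 to R21, none falls in the reported tmax range, against 6 in-range time points for each of ECG, vital signs and PK. The 6 h draw is 2 to 4.5 h after tmax for the usual and latest observed values. Under the log-linear assumption it sits at about 57% to 60% of peak after the single dose and 50% to 53% at steady state for the usual tmax, and at 67% to 76% if tmax is 4 h. That is substantial exposure, not trough, but it is not Cmax.

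The count depends only on Table 1 and its notes. What counts as around Cmax depends on preliminary, non-validated single-dose tmax data from healthy men, and patients may differ. It is not claimed that 2 h would detect more events than 6 h or that a DLT would be missed. This should be corrected because the risk/benefit rationale describes monitoring that the schedule lacks for two named hazards, and providing it is cheap.

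**What to change.** Add potassium and glucose to the existing 2 h PK draw on D1 and R14, and keep the 6 h sample. This puts 2 of 13 draws from D1 to R21 in the tmax range. Amend Table 1 note m and section 4.4.1 to match, change the count in Table 3 note a from 2 samples to 4, and restate the Table 3 volumes.

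The cost is two small tubes per patient at draws that already take place, with no new venepuncture. The protocol gives no tube size for this sample. Assuming 2 to 5 mL, the addition is 4 to 10 mL. The planned approximate maximum rises from 57 + 144 = 201 mL to 205–211 mL without optional samples, and from 201 + 9 + 18 = 228 mL to 232–238 mL with them. Safety volumes vary by site (Table 3 note c), so these totals are a guide only. Section 5.4 requires the amendment to be notified to or approved by each Ethics Committee.

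If the sponsor has a reason to prefer 6 h, such as an expected delay in effect, the minimum is to state it and reword section 3.2.2 to describe a 6 h sample. That is consistent but gives weaker monitoring than the rationale now offers.
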